To target the appraisal mechanisms and emotion experiences the attention bias modification task (ABM) was developed (Browning et al., 2012). Several Norwegian studies have documented that ABM training has the potential to modify attentional biases in depression (Jonassen et al., 2019) and anxiety (Kraft et al., 2019) as well as increasing motivation for daily life activities (Kraft et al., 2019). The ABM has also been used in combination with acceptance and commitment therapy in persons reporting depressive symptoms (Østergaard et al., 2019). The combination of ABM and ACT and ACT alone similarly decreased depressive symptoms after treatment and during follow up. Cognitive training has been shown to improve the specific cognitive functions targeted in the training, however the degree to which effects generalize to working life and daily life functions is still questioned (Melby-Lervåg, 2016).

The quantitative aim of this pilot study is to compare VR training and ABM training to investigate whether the different training forms result in different results measured with work-related outcomes and cognitive outcomes. The qualitative aim of this pilot study is to investigate the patients' experiences with the usage of VR.

Objectives - quantitative

The objective of this study is to investigate whether VR and ABM training increases work ability, work-related self-efficacy, attention and reduces symptoms of depression and anxiety and consequently change an attentional bias from negative to positive stimuli. We will compare patients receiving work-related interventions + VR, work-related interventions + ABM training and work-related interventions only. We will also investigate whether positive changes in attentional bias are

associated with increased work participation. Self-reported work ability, self-efficacy, depression, anxiety and objective computerised cognitive and emotional testing will be assessed at baseline (start rehabilitation/treatment) and at posttest (end rehabilitation/treatment).

Objectives - qualitative

The objective of this part is to investigate the experiences in using VR. R&D personell will make individual interviews with five patients at each of the three clinics involved in piloting VR. The aim of the interviews will be to capture how the patients experienced the VR activity, the demands of the VR activity, how VR has influenced different aspects of health and whether VR has influenced the abilities to return to work.

STUDY PLAN

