Individuals eligible for inclusion will be those between 18 – 67 years, on sick leave, work assessment allowance, disability pension receiving work-related rehabilitation or treatment at seven clinics with either an ICPC-2 (International Classification of Primary Care, Second edition) within the L (musculoskeletal), P (psychiatric) or A (unspecific disorders) categories or ICD-10 diagnosis within the F (mental and behavioral disorders), M (Diseases of the musculoskeletal system and connective tissue) or other diagnoses. *Exclusion criteria:* 1) Applying for full disability pension; 2) Unable to complete the measures and receive instructions in Norwegian.

Design and sampling

This is a non-randomised controlled experiment where we aim to recruit 20 patients from each of the six clinics involved in ABM training and up 100 from each of the clinics involved in VR. That is, 10 receiving ABM training and 10 in the control group, and 60 receiving VR and 40 in the control group. The participants will complete the questionnaires and cognitive measures one the day of arrival and on the penultimate or ultimate day of the rehabilitation/treatment. The measures will take

approximately one hour to complete at each measurement point and will not interfere with the participation in the rehabilitation/treatment.

In the qualitative part of this pilot, it is aimed to recruit 15 patients, five at each of the three clinics.

Self-reported questionnaire measures

Kvalitetsregisterkjema fra Nasjonal kompetansetjeneste for arbeidsrettet rehabilitering

Work Ability (Ahlstrom et al., 2010)

Return to work self-efficacy (Gjengedal et al., 2021; Nøttingnes et al., 2019)

Expectation about return to work (Løvvik et al., 2014)

Hospital Anxiety and Depression Scale (Zigmond & Snaith, 1983)

Computerised cognitive and emotional measures

Rapid Visual Information Processing (Cambridge Cognition, 2020) (**VR group and ABM group**)

Spatial Working Memory (Cambridge Cognition, 2020) (**VR group and ABM group**)

Stop Signal Task (Cambridge Cognition, 2020) (**VR group and ABM group**)

Attention Bias Assessment Task (Browning et al., 2012) (**ABM group only**)

Qualitative measures

Interview guide (National Advisory Unit on Occupational Rehabilitation, 2022)

Primary outcome measure

1) Work ability and expectations to return to work

2) Depression and anxiety

Secondary outcome measures

2) Cognitive and emotional performance assessed with the computerised measures

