3. Test 1: During the next two days the participants is administered three attention tests in front of a computer screen. It takes about 30 minutes to complete the tests. The participants also complete questionnaires about their work and health situation, as well as background information such as your age, education, marital status, type of job and work and benefit situation. It takes about 30 minutes to complete the questionnaires.
4. Test 2: On the third or second but last day of rehabilitation/treatment the participant completes the same tests and questionnaires as described above.
5. In the period between test 1 and test 2, all participants undergo VR activities or attention bias modification training on an Ipad/tablet. Each training session lasts for about 15 minutes and is carried out twice a day from Monday to Friday during rehabilitation/treatment or adjusted according to patients' needs and capabilities as well as the already existing rehabilitation programme at each participating clinic.
6. The participants in the control group complete test 1 and 2 but do not receive the added intervention described in 5.
7. R&D personell at each of the three clinics using VR will approach participants each after test 2 (sequence number 4) asking them if they would like to volunteer to take part in an interview about the experiences in using VR.

Power

A priori power calculations for F tests using G*Power (Faul et al., 2007) were performed to check which sample size was required to detect differences between groups in scores on work and health questionnaires using repeated-measures analysis of variance (pretest to posttest changes). Results indicated that with a power of 0.90, moderate effect size set at 0.25 and a two-tailed alpha level of 0.05 (Cohen, 1988), the total number of participants needed would be 44 in each group.

Study period

1 January 2022 to 1 June 2026.

Main study

This pilot study will inform whether we need to make adjustment or changes to the main study expected to commence 1 August 2024 and with particular reference to the following criteria:

- Is the main study feasible
- What changes should be made to the protocol of the main study
- What specific changes and amendments should be made to the design of the main study
- What specific recommendations to the main study are provided by the collaborating clinics and how do we deal with them and implement them in the main study

Dissemination

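### The stated 90% power with 44 per group for a moderate between-group difference in pre-post change is not supported by any calculation found to give 44

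*Protocol*

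**What the plan says.** The Power section of the protocol reports "A priori power calculations for F tests using G*Power" to find the sample size for detecting differences between groups on work and health questionnaires, "using repeated-measures analysis of variance (pretest to posttest changes"). The inputs given are "with a power of 0.90, moderate effect size set at 0.25 and a two-tailed alpha level of 0.05", with a standard power-analysis text cited. The result is 44 in each group, although the same sentence also calls it a total.

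The contrast so described is a difference between groups in change over two measurements, that is, a group-by-time effect. This agrees with Objectives - quantitative, which compares VR, ABM and rehabilitation only, measured at baseline and posttest.

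Design and sampling sets recruitment per clinic at "10 receiving ABM training and 10 in the control group, and 60 receiving VR and 40 in the control group", with six ABM clinics and three VR clinics (the VR figure is an upper limit).

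The protocol does not state which repeated-measures F test was chosen, the effect-size option, the number of groups entered, the assumed pre-post correlation, or what 0.25 means as a difference on any questionnaire.

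**The concern.** The convention that f = 0.25 is moderate belongs to differences between group means, where with two groups it equals 0.5 SD. The same number entered for a group-by-time effect need not mean the same thing. If it means a much larger difference in change, or if the calculation was for a different test, then the 90% does not apply to what the section says it applies to.

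A project report and one article are planned. A reader of a null result could take the power statement to mean that a moderate benefit was very likely to have been detected. The Main study section says the pilot will inform the main study's design, so a figure that does not describe its own contrast should not stand uncorrected.

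**Working it through.** **Inputs.** From the Power section: two-sided alpha 0.05, power 0.90, f = 0.25, result 44. From Objectives - quantitative: two measurements (m = 2). Assumed, because not stated: pre-post correlation ρ, shown over a range; number of groups k; test and option; moderate taken as 0.5 raw SD.

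**Step 1. Which settings give 44?** f² = 0.0625 throughout, and power comes from the noncentral F distribution.

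- *Group-by-time interaction, default option*: λ = f²·N·m/(1 − ρ).
  - k = 2, ρ = 0, N = 88: λ = 0.0625 × 88 × 2 / 1 = 11.0, power 0.906. This is 44 per group.
  - k = 2, ρ = 0.5, N = 44: λ = 0.0625 × 44 × 2 / 0.5 = 11.0, power 0.8997. This is 44 in total, to rounding; strictly N = 46 is needed (0.912).
- *Within-factor test, one group*, ρ = 0.5, N = 44: λ = 11.0 with 1 and 43 df, power 0.90003. N = 43 gives 0.893, so 44 is exactly the smallest N.
- *Between-factor test*: λ = f²·N·m/(1 + ρ).
  - k = 2, ρ = 0, N = 88: λ = 11.0, power 0.906 (44 per group).
  - k = 3, ρ = 0.25, N = 132: λ = 0.0625 × 132 × 2 / 1.25 = 13.2, power 0.906 (44 per group).
- *Do not give 44*: the three-group interaction, default option (35 per group at ρ = 0, 18 at ρ = 0.5), and the two-group interaction with effect size as in Cohen (86 per group).

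**Step 2. What does 0.25 mean in each?**

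- *Interaction, default option.* In a 2 × 2 layout, a difference in mean change of D raw SD gives cell interaction effects of ±D/4. Hence f = D/4, and f = 0.25 is D = 1.0 SD. Check: the SD of change is √(2(1 − ρ)) = 1 at ρ = 0.5, and a two-sample t-test on change with D = 1.0 and 23 per group has power 0.912, the same as the F test with N = 46.
- *Within-factor, one group.* f = d/2, so 0.25 is a 0.5 SD pre-post change, a moderate effect on its usual scale. It involves no comparison between groups.
- *Between-factor.* 0.25 is on its usual scale for group means, but the test compares scores averaged over the two times, not change.

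**Step 3. Power of 44 versus 44 for a 0.5 SD difference in change.** The noncentrality is δ = [0.5/√(2(1 − ρ))] × √(n₁n₂/(n₁ + n₂)), with √(44 × 44/88) = 4.690 and 86 df.

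| ρ | SD of change | δ | Power |
|---|---|---|---|
| 0 | 1.414 | 1.658 | 37.5% |
| 0.3 | 1.183 | 1.982 | 50% |
| 0.5 | 1.000 | 2.345 | 64% |
| 0.7 | 0.775 | 3.028 | 85% |
| 0.75 | 0.707 | 3.317 | 91% |

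For 90% power, the numbers needed per group are 170, 119, 86 and 52 at ρ = 0, 0.3, 0.5 and 0.7. If 44 is a total (22 versus 22), power at ρ = 0.5 is 37%.

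**Step 4. Power at the recruitment targets, 0.5 SD, before dropout and clustering.** ABM: 6 × 10 = 60 trained and 60 own-clinic controls. VR: up to 3 × 60 = 180 trained and 3 × 40 = 120 controls. Pooled controls: 60 + 120 = 180.

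| Comparison | ρ = 0.3 | ρ = 0.5 | ρ = 0.7 |
|---|---|---|---|
| ABM vs own-clinic controls, 60:60 | 63% | 78% | 94% |
| ABM vs pooled controls, 60:180 | 81% | 92% | 99% |
| VR vs own-clinic controls, 180:120 | 95% | 99% | >99% |

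**The case against.** **The cause is not known.** A reader might infer that the sponsor entered 0.25 on the wrong scale and so sized the study for a 1 SD difference. The documents do not establish that. The one-group within-factor test gives exactly 44 at ρ = 0.5 with 0.25 on its ordinary 0.5 SD scale, and it fits the mention of pretest-to-posttest change. This stands as far as the cause goes. It does not rescue the claim, because that test says nothing about a difference between groups.

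**The ABM comparison may not fall short.** A reader might also infer that ABM is underpowered as planned. That depends on comparing 60 with 60. Objectives - quantitative and Gender issues both describe three groups, which can be read as one pooled control group. With 180 controls, power at ρ = 0.5 is 92%. This stands: a shortfall at the recruitment targets is conditional, not shown.

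**A high correlation would help.** At ρ of about 0.75, 44 per group does give 90% for 0.5 SD. But at that correlation the default interaction calculation has λ = 0.5N, which already equals 11 at N = 22, so it would not have returned 44.

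**The background evidence does not size the effect.** It is tempting to cite "The combination of ABM and ACT and ACT alone similarly decreased depressive symptoms after treatment and during follow up" as a sign that the added effect is small. That sentence gives no effect size and concerns a different combination of treatments, so nothing here rests on it.

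**It is a pilot.** The study is non-randomised, and its criteria for the main study concern feasibility and design. Nothing says the calculation will be reused. This limits the consequence, but the stated power remains wrong as written.

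**Conclusion.** The point holds in limited form: the Power section's 90% for a moderate between-group difference in change with 44 per group is unsupported under each setting found to return 44. Either 0.25 stands for about a 1 SD difference in change, or the test is not of that contrast. For 0.5 SD, 44 per group gives about 50% to 85% power over correlations of 0.3 to 0.7.

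This rests on two assumptions: that moderate means 0.5 raw SD, and the correlation range. The powers in Step 4 also take the clinic counts in Design and sampling at face value. The documents support neither a definite statement of how the 44 arose nor a conclusion that the planned ABM comparison is underpowered.

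**What to change.** Restate the power paragraph for the group-by-time contrast. Give the G*Power test and effect-size option, the number of groups entered, the assumed pre-post correlation, and the target difference in change in raw SD (or scale points). Say whether 44 is a total or per group. Drop either the word moderate or the 90% claim for 44 per group.

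Then name the comparison actually intended (own-clinic or pooled controls) and report power at the recruitment targets for it over a range of correlations, as in Step 4, with allowance for dropout and clustering. The 1 SD conversion and any single power figure should be written in only once the sponsor has confirmed the settings used.

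The cost is a recalculation and a rewritten paragraph. Enrolment need not change. The drawback is a less favourable stated power.
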